1.1 PROTOCOL ABSTRACT AND SUMMARY

1.2 Protocol Abstract

Estrogen receptor negative (ER(-)), progesterone receptor-negative (PR(-)) breast cancer represents approximately 25 - 30% of all breast cancers. Unlike estrogen receptor-positive (ER(+)) breast cancer, patients with ER(-)/PR(-) disease are not candidates for current anti-hormonal strategies. The biology of ER(-) disease is poorly understood and with the exception of trastuzumab for Her2/neu-positive tumors, targeted therapy options are limited. Genome-wide expression analysis has revealed a subset of ER(-)/PR(-) breast cancers that share a gene expression profile with hormone receptor-positive tumors¹. Among these shared genes is the androgen receptor (AR). In-vitro studies of androgen blockade demonstrated a reduction in growth of ER(-)/PR(-)/AR(+) breast cancer cells. Clinical investigation of androgen blockade in breast cancer patients is therefore a rational therapeutic strategy.

The primary objective of this Phase II study is to evaluate the efficacy of bicalutamide (CasodexTM, Astrazeneca), a well-tolerated anti-androgen used in prostate cancer, in women with ER(-)/PR(-)/AR(+) metastatic breast cancer. Efficacy will be measured by the response rate (RR), including those patients with a demonstrated complete response (CR), partial response (PR), or stable disease (SD) after 6 months from the first day of therapy. Secondary objectives include progression-free survival (PFS), safety and correlative studies. Correlative studies, including peripheral blood hormone levels and selected immunohistochemical markers, will further characterize the biology of this novel subtype of breast cancer. This is an important study for the field of breast cancer research because bicalutamide may allow a greater number of patients with breast cancer the option of treatment with hormonal therapy instead of, or in addition to, chemotherapy.

1.3 Protocol Summary

This is a multicenter, open-label, phase II study to evaluate the antitumor activity and safety of bicalutamide administered orally daily to patients with ER(-)/PR(-)/AR(+) metastatic breast cancer. Patients with measurable or non-measurable, metastatic breast cancer are eligible. Prior neo-adjuvant or adjuvant chemotherapy is permitted. There is no restriction on prior chemotherapy or hormonal therapy. Prior therapy with trastuzumab is allowed but may not be administered while on study.

Patients with metastatic, ER(-), PR(-) breast cancer may consent to androgen receptor testing while on breast cancer-directed treatment. If they are found to have AR(+) disease, they will be considered potentially eligible for treatment on study. At the time their treating physician determines they require a change in therapy, they may consent to participate in this study if they meet remaining eligibility criteria.

Eligible patients who have consented to trial participation will receive bicalutamide at a dose of 150mg PO daily. Up to two dose reductions of 50mg each will be allowed for grade 3 or 4 toxicity as specified by the protocol. The primary aim of the study is to evaluate the efficacy of

IRB#: 07-022A(13)

bicalutamide after 6 months of therapy. The study is a phase II design with a planned enrollment of 28 patients. If 4 or more patients demonstrate a response (defined as either a CR, PR or SD) after 6 months of therapy, bicalutamide will be considered a feasible and potentially promising therapy. Patients with progression of disease will be withdrawn from the study. Treatment may continue after 6 months in the absence of progression of disease or unacceptable toxicity.

Based on studies of bicalutamide in men with prostate cancer, an oral daily dose of 150 mg per day has been selected for this study. In men, the pharmacodynamic, pharmacokinetic, safety and efficacy data support this dose for monotherapy. Studies of doses up to 600 mg failed to show dose-related increases in adverse events. This study will not aim to provide extensive pharmacokinetic and pharmacodynamic data on different dose levels. It will not aim to recapitulate data from previous studies performed in men. Rather, this is a straightforward extrapolation of studies performed in men, to test this hormonal agent in women based on a rational biologic hypothesis. While there may be differences seen with its use in women, this study has been designed with a dose reduction schema and early stopping rules for toxicity. Additionally, correlative studies will include serum hormonal levels to further characterize differences seen in women.

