3.4 Rationale for bicalutamide study dose selection

Though bicalutamide has not been well tested in women, the extensive studies of this drug in men with prostate cancer demonstrating good tolerability provide support for its use in women. The selection of a dose of 150 mg per day is based on pharmacokinetic, pharmacodynamic and safety data from studies performed in men with prostate cancer. Notably, studies of doses above 150 mg (up to 600 mg) failed to show dose-limiting toxicity. The dose of 150 mg reflects an optimal steady-state concentration and PSA-lowering effect in men with prostate cancer.

Because there may be differences seen with the use of bicalutamide in women, this study has been designed with a dose reduction schema for toxicity. Correlative studies include a panel of serum hormonal studies that will provide information on differences seen in the hormonal/metabolic pathways in women. The goal of this study is to test the hypothesis that androgen blockade in women with ER(-)/PR(-)/AR(+) breast cancer (ER(-) Class A) is an effective hormonal treatment. This study will not perform pharmacokinetic and pharmacodynamic studies.

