4.3 Intervention

Patients will receive bicalutamide at a dose of 150mg PO daily. Patients will be seen monthly for an assessment by a care provider familiar with the protocol. Clinical assessment and serum studies will be performed per protocol (See Time and Events Schedule, Section 10). Patients may be seen before their scheduled monthly follow-up if they are experiencing any adverse effects or symptoms that may be consistent with progression of disease. Patients will undergo a radiologic extent of disease evaluation (EOD) every 3 months. An EOD may be performed earlier than a 3 month interval if progression of disease is suspected. Response will be evaluated using RECIST criteria as complete response (CR), partial response (PR), stable disease (SD) or progressive disease (PD).

If a patient experiences unacceptable toxicity at the initial dose level, up to two dose reductions of 50mg each will be permitted. Dose reduction of bicalutamide from the initial dose of 150mg PO daily to100mg PO daily will occur for an individual patient if that patient experiences unacceptable toxicity. A second dose reduction of 50mg is acceptable. Toxicities will be graded using the NCI Common Terminology Criteria for Adverse Events (CTCAE) Version 3. Treatment may be delayed no more than 2 weeks to allow recovery from acute toxicity. In the event of a treatment delay exceeding 2 weeks, the patient will be withdrawn from the study.

[figure not shown]
A patient will be withdrawn from the study in the following situations:

- For an unacceptable toxicity, defined as a Grade 3 or 4 non-hematologic toxicity after 2 (50 mg) dose reductions (see Section 11.2.5); or
- For unacceptable toxicity that fails to resolve after a maximum treatment delay of 2 weeks; or
- Progression of disease

Treatment with bicalutamide will continue until one or more of the criteria for withdrawal from study are met. After 6 months of treatment, patients will be considered responders if they achieve a CR, PR or SD by RECIST criteria. At the investigator's discretion, and in the absence of disease progression by RECIST criteria, treatment with bicalutamide may continue beyond 6 months. Study drug is provided by AstraZeneca.

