10.0 EVALUATION DURING TREATMENT/INTERVENTION

Day 0 and every 4 weeks (+/- 5 days), the following clinical and laboratory assessments must be done prior to continuation of treatment with bicalutamide:

- History and physical examination, including:
 - Vital signs
 - ECOG performance status
 - o Weight
 - Concomitant medications
- Laboratory assessments, including: (screening labs can be used as Day 0 labs)
 - CBC with differential and platelet count
 - Comprehensive metabolic panel (Na, K, Cl, CO2, BUN, Creatinine, Ca, Glucose, Total Protein, Albumin, Alkaline Phosphatase, Total Bilirubin, AST and ALT)
- Adverse Event Evaluation (toxicity assessment using the NCI CTC version 3)
- Blood for correlative study of hormonal levels including estradiol, total testosterone, free testosterone, and sex-hormone binding globulin will be performed at baseline, after Cycle #1 and at the end of study. (See further description below)

Every 12 weeks (+/- two weeks), tumor assessments will be performed. Patients with measurable disease will be evaluated for complete response (CR), partial response (PR), stable disease (SD) or progressive disease (PD) using RECIST criteria, using the same modality of imaging performed at baseline. Patients with non-measurable disease will be evaluated for either stable disease or progressive disease. Responders and stable disease patients will continue on study unless they develop unacceptable toxicity. Progressive disease or unacceptable toxicity (after a maximum of two dose reductions) will be the criteria for treatment failure and discontinuation from the study.

Response assessment will include:

- Radiologic scans of disease sites (e.g. CT scan of chest, abdomen and pelvis and PET or bone scan if there are bone lesions identified on pre-study bone imaging)
- Measurement of all target lesions that are followed by physical examination
- Patients achieving a CR or PR must have confirmation of response at least 4 weeks following the initial response determination.
- End-of-Study (EOS) Evaluation: At the time patients are removed from study, laboratory and clinical evaluations to assess adverse events (AEs) will be performed. Serum hormone panel including estradiol, free and total testosterone and serum hormone binding globulin will be collected. Radiologic studies for antitumor response will be repeated if they have not been performed within the previous 28 days.

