11.3.2 Breast Pain/Tenderness

If \geq grade 3 breast pain occurs, that is not controlled with non-opioid pain medications (NSAIDs, Tylenol), bicalutamide should be withheld until resolution to \leq to grade 1, then reinstituted at the next lower dose level. If \geq grade 3 breast pain occurs at a reduced dose level, and is not controlled with non-opioid pain medications, bicalutamide should be withheld until resolution to \leq grade 1, then reinstituted at the next lower dose level. If, after 2 dose reductions (to 50mg PO daily), \geq grade 3 breast pain persists, opioid pain medicine is encouraged. If symptoms persist, patient may be referred to a radiation oncologist (if no breast irradiation to palliate symptoms. If none of these interventions successfully alleviates symptoms, and if \geq grade 3 breast pain persists, then patient will be discontinued from study. Toxicity will be reported, and patient will be evaluated as unable to tolerate bicalutamide. If \leq grade 2 breast pain persists, patient may elect to stop treatment on study, or to continue. If patient chooses to discontinue study treatment, toxicity will be noted; however, this will not constitute unacceptable toxicity for purposes of adverse event reporting.

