14.0 BIOSTATISTICS

This is a multicenter, open-label, phase II study to evaluate the efficacy of bicalutamide administered orally daily to patients with ER(-)/PR(-)/AR(+) metastatic breast cancer. The primary endpoint of this trial is the response rate (RR), defined as the total number of patients who demonstrate a complete response (CR), partial response (PR) or stable disease (SD) (after 6 months from the first day of treatment) divided by the total number of patients treated. Upon

IRB#: 07-022A(13)

completion of the study, the RR will be estimated via the observed response rate and an exact confidence interval will be constructed. The response rate for patients with only measurable disease will be reported separately as the number of patients who demonstrate a CR, PR or SD >6months divided by the number of patients with measurable disease treated with bicalutamide. For this trial, a target response rate of 20% or higher is considered promising. A target response rate below 5% is considered unacceptable.

This study is designed as a single-stage, phase II which requires a total of 28 patients. If 4 or more patients have a CR, PR or SD after 6 months from the first day of treatment, bicalutamide will be considered feasible and will merit further clinical study. With 28 patients, this design discriminates between true response rates of $\leq 5\%$ and $\geq 20\%$ at a Type I error of 5% and a Type II error of 16%.

Secondary objectives of this study include estimating median progression-free survival at 6 months and describing the rate of selected non-hematologic and hematologic toxicities. Progression-free survival will be estimated by the Kaplan-Meier method. Selected toxicities will be described by frequency and grade, by cycle and overall cycles, with the maximum grade over all cycles used as the summary measure per patient. The safety endpoint will also be measured as the percentage of patients who are able to tolerate daily treatment with bicalutamide after a maximum of 2 (50mg) dose reductions from the starting dose of 150mg, for 6 months from the first day of treatment.

Data analysis plan:

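### The Protocol Summary offers toxicity stopping rules as a safeguard for 150 mg in women, but the protocol states no trial-level toxicity criterion

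*Combined protocol and SAP*

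**What the plan says.** Section 1.3 concedes that the drug may behave differently in women and answers that "this study has been designed with a dose reduction schema and early stopping rules for toxicity". The dose rationale in section 3.4 makes the same argument but names one safeguard only: "this study has been designed with a dose reduction schema for toxicity". Section 3.3 reports that bicalutamide had not been tested in women as a cancer treatment, nor at any dose above 25 mg per day.

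The provisions that bear on toxicity are these:

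- **Section 4.3** lists the grounds for withdrawing a patient, among them: "For an unacceptable toxicity, defined as a Grade 3 or 4 non-hematologic toxicity after 2 (50 mg) dose reductions". Toxicity that outlasts a 2-week delay is another.
- **Sections 11.3.1 to 11.3.5** give hold, reduction and discontinuation rules by type of toxicity. Section 13.0 lists reasons for removing a patient.
- **Section 14.0** states: "This study is designed as a single-stage, phase II which requires a total of 28 patients". Its one decision criterion is efficacy, 4 or more of 28. On safety it says: "The safety endpoint will also be measured as the percentage of patients who are able to tolerate daily treatment with bicalutamide", over 6 months and after at most two reductions. It attaches no acceptable level and no interim look to that percentage. Other toxicity results are summarized by frequency and grade.
- **Data and Safety Monitoring (within section 16)** names an institutional committee for phase I and II trials and leaves each protocol's monitoring procedures to be settled at activation. It gives no study-specific trigger.
- **Section 10.0** sets the visit schedule: "Day 0 and every 4 weeks (+/- 5 days), the following clinical and laboratory assessments must be done". Adverse event evaluation is on that list.

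**The concern.** Section 1.3 relies on two safeguards to justify carrying a dose over from men to women. The first can be found and followed. The second cannot be found at the level of the trial. From this protocol alone, a reader cannot tell whether any number of severe toxicities among the first patients would interrupt enrollment. Followed as written, all 28 patients could be enrolled whatever the toxicity rate turns out to be.

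This matters more than usual here because there is no tolerability experience in women near the study dose, and safety is a stated secondary objective. The adverse event data that a pause rule would need are already collected every 4 weeks.

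**Working it through.** **1. The plan's own design figure.** Inputs from section 14.0: N = 28, success at 4 or more, rates 5% and 20%. Exact binomial: P(X ≥ 4 | 28, 0.05) = 0.0491 and P(X ≥ 4 | 28, 0.20) = 0.8398, so the type II error is 0.1602. The stated 5% and 16% reproduce. Nothing below alters them.

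**2. Search for a trial-level toxicity criterion.**

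| Place | What it governs | Acts on |
|---|---|---|
| 4.3 | withdrawal after two reductions, or after a 2-week delay | one patient |
| 10.0 | treatment failure and discontinuation | one patient |
| 11.3.1–11.3.5 | hold, reduce, discontinue | one patient |
| 13.0 | removal list | one patient |
| 14.0 | efficacy criterion; descriptive toxicity | trial, but no toxicity limit |
| Data and Safety Monitoring | committee oversight, procedures set at activation | trial, but no trigger |

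No toxicity rate, boundary, interim safety look or accrual pause is stated, so there is no plan figure for toxicity to reproduce.

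**3. Dose ratio.** 150 mg (section 4.3) / 25 mg (section 3.3) = 6.

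**4. What a simple rule would do.** Let X(n) be the number of affected patients among the first n treated. Pause at the first n with X(n) ≥ b(n), where b = 3 for n ≤ 10, 5 for n = 11–19 and 7 for n = 20–28. The documents give no rate for this event in women, so every true rate p is an assumption.

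One piece can be checked by hand. The boundary is 3 throughout the first 10, so the chance of pausing by patient 10 is P(X(10) ≥ 3). At p = 20% this is 1 − (0.1074 + 0.2684 + 0.3020) = 0.322. The later boundaries bring the total to 0.484.

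Exact enumeration over all paths, with outcomes known immediately and accrual assumed not to resume after a pause:

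| True rate p | Pause probability | Mean treated | Affected patients spared = p × (28 − mean treated) |
|---|---|---|---|
| 5% | 0.012 | 27.8 | 0.01 |
| 6% | 0.021 | 27.6 | 0.02 |
| 10% | 0.088 | 26.4 | 0.16 |
| 15% | 0.256 | 23.8 | 0.6 |
| 20% | 0.484 | 20.2 | 1.6 |
| 25% | 0.701 | 16.4 | 2.9 |
| 30% | 0.856 | 13.0 | 4.5 |

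With no rule, 28 are treated and 28p are affected: 28 × 0.20 = 5.6 and 28 × 0.30 = 8.4.

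**5. Delayed outcomes.** Suppose L further patients enter before each outcome is known (L is an assumption; no accrual rate is given). From 400,000 simulated trials:

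| p | L | Mean treated | Expected affected | Affected with no rule |
|---|---|---|---|---|
| 20% | 4 | 22.0 | 4.4 | 5.6 |
| 20% | 8 | 23.7 | 4.7 | 5.6 |
| 30% | 4 | 16.3 | 4.9 | 8.4 |
| 30% | 8 | 19.4 | 5.8 | 8.4 |

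With L = 8, the chance that the pause comes before all 28 have entered is 0.43 at 20% and 0.78 at 30%.

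**6. Sensitivity to the boundary.** Three tighter boundaries use a Beta(0.5, 0.5) prior. From the third patient on, they pause when the posterior probability that the rate exceeds 10% is above 0.95, or that it exceeds 15% is above 0.85 or 0.90. They pause with probability 4–7% at p = 6%, 14–20% at 10%, 55–68% at 20% and 88–94% at 30%. More sensitivity at high rates costs more needless pauses at low ones.

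**The case against.** **The phrase may mean patient-level stopping.** The same sentence opening governs the dose reduction schema, which is wholly patient-level, so the grammar does not settle the matter. Reduce the dose, then stop treatment, is a coherent pair, and the protocol has both. This reading is possible. The separate listing as a property of the study design, and its absence from the otherwise parallel sentence in section 3.4, lean the other way without proving it. On either reading section 14.0 has no trial-level criterion.

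**Oversight exists.** A reader might infer that the trial ran with nobody placed to act on toxicity, or that no trigger was ever set. The documents do not support either inference. A monitoring committee is named and also reviews patients treated at collaborating institutions. Serious adverse events go to the IRB within 5 calendar days. Fatal or life-threatening ones go to the drug supplier by the next business day. Participating sites report serious events within 3 days and deaths immediately (section 17). Monitoring procedures were to be set at activation, in material not included here. What stands is narrower: this protocol states no threshold.

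**The gain may be small.** In men at 150 mg, withdrawal for adverse events was 6% in two phase III trials. In the early-disease program it was 29.3%, of which 16.8 percentage points were for breast pain or gynecomastia (section 3.2). Hepatitis or marked enzyme rises leading to discontinuation occurred in about 1% (Appendix A). Doses up to 600 mg in men showed no dose-related increase in adverse events, and the 25 mg figure comes from studies of polycystic ovary disease and hirsutism, not from a tolerability ceiling. All of this is fair. None of these figures is a rate of the proposed event in women, but a low true rate is plausible, and then the rule spares almost no one.

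**Conclusion.** The point holds in a limited form. Section 1.3 leans on a safeguard that, on its more natural reading, the protocol does not contain: the toxicity rules are patient-level, section 14.0 has no trial-level toxicity criterion, and committee oversight is described without a trigger. It would be too strong to conclude that patients were unprotected or that no criterion existed anywhere.

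The size depends on assumed rates. With immediate outcomes the proposed rule spares 0.02 affected patients at a true rate of 6%, 0.16 at 10%, 1.6 at 20% and 4.5 at 30%. If 8 more patients enter before outcomes are known, the last two fall to about 0.9 (5.6 − 4.7) and 2.6 (8.4 − 5.8). So the benefit is slight below about 15% and moderate at 20–30%. The change is worth making because it is cheap; confidence is medium.

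**What to change.** Add a short paragraph to section 14.0 that pauses accrual for review by the Data and Safety Monitoring Committee when the number of affected treated patients reaches 3 within the first 10, 5 within the first 19, or 7 within 28. A patient is affected, and counts once, with any of:

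- treatment-related grade 3 or higher non-hematologic toxicity, including at the 150 mg starting dose and even if it resolves on hold;
- withdrawal for toxicity required by section 4.3 or 11.3;
- treatment-related death.

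Voluntary stopping for grade 2 or lower breast pain would not count, in line with section 11.3.2 ("this will not constitute unacceptable toxicity for purposes of adverse event reporting"). State the operating characteristics, with an allowance for delayed outcomes, and align sections 1.3 and 3.4 with the rule. If an equivalent criterion was set at activation, cite it in section 14.0 instead. Rewording section 1.3 alone would remove the mismatch but add no safeguard.

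The cost is one paragraph, using adverse event data already collected each cycle, and a chance of a needless pause: about 2% at a true rate of 6% and 9% at 10%. A pause for review does not end the trial, and N = 28 and the 4-responder criterion are untouched.

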2.1 OBJECTIVES AND SCIENTIFIC AIMS

2.2 Primary Objective

The primary objective of this study is to:

• Evaluate the efficacy of treatment with bicalutamide at 6 months for patients with ER(-) /PR(-)/AR(+) metastatic breast cancer in terms of response (CR, PR) and SD.

